5.2.6 Assessment of adverse events

5.2.6.1 Definitions of AEs

5.2.6.1.1 Adverse event

An AE is defined as any untoward medical occurrence in a patient or clinical investigation subject administered a medicinal product and which does not necessarily have to have a causal relationship with this treatment.

An AE can therefore be any unfavourable and unintended sign (including an abnormal laboratory finding), symptom, or disease temporally associated with the use of a medicinal product, whether or not considered related to the medicinal product.

The following should also be recorded as an AE in the CRF and BI SAE form (if applicable):

- Worsening of the underlying disease or of other pre-existing conditions
- Changes in vital signs, ECG, physical examination, data on SMBG log and laboratory test results, if they are judged clinically relevant by the investigator.

If such abnormalities already exist prior to trial inclusion, they will be considered as baseline conditions and should be collected in the eCRF only.

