Drug-induced liver injury (DILI)	No risk of DILI was identified for empagliflozin. However, DILI generally can be severe and lead to fatal outcome or need of liver transplant. Therefore, careful monitoring and assessment of patients for potential DILI are needed.	Parameters for potential liver injury are included in the safety laboratory. Cases of liver impairment are defined as an AESI. Severe cases of liver impairment are adjudicated. (See Sections 5.2.3 , 5.2.6.1.4 and 8.7 ; details are also described in the adjudication charter).
Renal safety	In clinical trials in patients with DM, the incidence of renal impairment was similar to placebo. An initial decrease of estimated glomerular	Parameters for potential renal impairment are included in the safety laboratory.

Table 1.4.2:1 Known and potential risks of clinical relevance for the study population (cont.)

Possible or known risks of clinical relevance for this trial	Summary of data, rationale for the risk	Mitigation strategy
	
filtration rate (eGFR) was seen in patients treated with empagliflozin, which improved during continuous treatment or discontinuation of empagliflozin.
 
Cases of renal impairment, including those requiring dialysis, were reported in patients using SGLT2-inhibitors. Due to the renal mode of action and risk of volume depletion, the renal safety should be monitored.
	Cases of renal impairment are defined as an AESI (see Sections 5.2.3 and 5.2.6.1.4).
Trial procedures		
The patients who take placebo have a higher probability of treatment failure, i.e., of increase in HbA1c.	50% of patients will receive placebo.	This study will have criteria for rescue therapy (refer to Section 4.2.2) and patient discontinuation from study medication to ensure an adequate treatment in case of any clinical concern (refer to Section 3.3.4).
Hyperglycaemia	50% of patients will receive placebo and these patients thus have a higher probability of treatment failure, i.e., of increase in FPG and HbA1c.	Blood glucose will be monitored with SMBG. Appropriate inclusion/exclusion criteria of HbA1c and FPG values, as well as criteria for rescue therapy and patient discontinuation will ensure an adequate treatment in case of any clinical concern.

Table 1.4.2:1 Known and potential risks of clinical relevance for the study population (cont.)

Possible or known risks of clinical relevance for this trial	Summary of data, rationale for the risk	Mitigation strategy

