3.3.4.1 Discontinuation of trial treatment

An individual patient will discontinue trial treatment if:

Proprietary confidential information © 2020 Boehringer Ingelheim International GmbH or one or more of its affiliated companies

- The patient wants to discontinue trial treatment, without the need to justify the decision.
- The patient has repeatedly shown to be non-compliant with important trial procedures and, in the opinion of both, the investigator and sponsor representative, is not willing or able to adhere to the trial requirements in the future.
- The patient needs to take concomitant medication that interferes with the investigational medicinal product. Please refer to Sections [4.2.1](#) and [4.2.2](#)
- The patient can no longer receive trial treatment for medical reasons (such as surgery, adverse events, or other diseases).
- Introduction of rescue therapy due to hyperglycaemia as described in Section [4.2.1](#) does not lead to sufficient treatment efficacy (rescue criteria still met). In this case, the reason for discontinuation will be classified as “lack of efficacy”
- Occurrence of hypoglycaemia that may put the patient at risk with continued participation (e.g., repeated hypoglycaemic episodes)
- Medically significant events that may put the patient at risk with continued participation (i.e., DKA, severe UTI including urosepsis, Fournier’s gangrene).

In case of a temporary reason, trial treatment should be restarted if medically justified, please see Section [4.1.4](#).

Patients who discontinue treatment prematurely will be followed up until the end of the trial as outlined in the [flowchart](#) and Section [6.2.2](#).

A patient can be discontinued from the trial after discussion between the sponsor and the investigator if the eligibility criteria are being violated.

Patients who discontinue or withdraw from the study during placebo run-in period and before being randomised at Visit 3 will be considered a run-in failure. They have to be recorded as in eCRFs and no further follow-up is required (except for AEs, if needed).

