7.8.1 Adverse Events

AEs will be coded using the latest version of the MedDRA coding dictionary at DBL. The analyses of AEs will be descriptive in nature. All analyses of AEs will be based on the number of patients with AEs (NOT the number of AEs). For analysis of multiple AE occurrences, data from the eCRF will be collapsed into an AE provided that all of the following applies:

- All AE attributes are identical (including LLT, intensity, action taken, therapy required, seriousness, reason for seriousness, relationship, outcome, AE of special interest and also additional information of specific AEs or AESIs).
- The occurrences were time-overlapping or time-adjacent (time-adjacency of 2 occurrences is given if the second occurrence started on the same day or on the day after the end of the first occurrence).

For further details on summarization of AE data, please refer to the guideline “Analysis and Presentation of Adverse Event Data from Clinical Trials” ([7](#)).

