7.8.1.1 Assignment of AEs to treatment

The analysis of adverse events will be based on the concept of treatment emergent adverse events. This means that all adverse events occurring between first drug intake until 7 days after last drug intake will be assigned to the first treatment received. All adverse events occurring before first drug intake will be assigned to 'pre-treatment' and all adverse events occurring after last drug intake + 7 days will be assigned to 'post-treatment'.

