7.8.1.2 AE summaries

An overall summary of adverse events will be presented.

The frequency of patients with adverse events will be summarised by treatment, primary SOC and PT.

AEs will also be reported by intensity. Separate tables will be provided:

- for patients with adverse events of special interest (AESI),
- for patients with serious adverse events,
- for patients with AEs leading to discontinuation,
- for patients with AEs leading to death,
- for patients with drug-related AEs.

The SOCs will be sorted according to the standard sort order specified by EMA, and PTs will be sorted by frequency (within SOC).

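### Worsening of diabetes counts as an adverse event, so the pooled AE totals include efficacy failures mainly from placebo and can dilute an overall AE excess on empagliflozin

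*Protocol*

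**What the plan says.** - **Recording.** Protocol 5.2.6.1.1 lists "Worsening of the underlying disease or of other pre-existing conditions" among the things to record as AEs, with no exemption for type 2 diabetes. Changes in laboratory results and in the SMBG log are also AEs "if they are judged clinically relevant by the investigator".
- **Expected imbalance.** Protocol Table 1.4.2:1, under hyperglycaemia: "50% of patients will receive placebo and these patients thus have a higher probability of treatment failure, i.e., of increase in FPG and HbA1c". It gives a direction but no rate.
- **Counting.** SAP 7.8.1 counts patients with at least one AE, not events. Under SAP 7.8.1.1, "all adverse events occurring between first drug intake until 7 days after last drug intake will be assigned to the first treatment received". There is no cut at the start of rescue medication.
- **Tables.** SAP 7.8.1.2: "An overall summary of adverse events will be presented". It adds a table by SOC and PT, a report by intensity, and separate tables that include one "for patients with AEs leading to discontinuation". None has a version without glycaemic-worsening terms.
- **Failed rescue.** Under protocol 3.3.4.1, when rescue does not bring glucose below the rescue criteria, "the reason for discontinuation will be classified as" lack of efficacy.

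**The concern.** In a placebo-controlled glucose-lowering trial, worsening glycaemia is the mirror image of efficacy. If it is also an AE, a treatment that works lowers its own AE count, and the overall AE comparison mixes benefit with harm in a predictable direction. The primary HbA1c analysis sets values after rescue to missing (protocol 7.2.2), but the AE totals make no such separation.

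What is at stake is how the any-AE row, the intensity breakdown and possibly the discontinuation row are read. A modest overall excess on empagliflozin in this elderly population could look smaller than it is. A reader cannot undo this from the PT rows. Those rows show how many patients had each glycaemic term, but not how many of them had no other AE.

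**Working it through.** **What can be checked.** The plan states no AE rate, so there is no figure to reproduce on this point. The only design input used is the arm size in protocol 7.5: 62 evaluable per arm, allowing 3% loss, gives 62 / 0.97 = 63.9, so 64 per arm. Every AE rate below is an assumption.

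**Any AE.** Let p be the proportion with a non-glycaemic AE and h the proportion with a glycaemic-worsening AE, assumed independent:

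any AE = 1 − (1 − p)(1 − h)

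With the same p in both arms, the shift in the difference (empagliflozin minus placebo) is −(1 − p)(h_placebo − h_empa). At p = 60%, a 10% v 2% split gives −0.40 × 0.08 = −3.2 points.

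| Glycaemic AEs, placebo v empagliflozin | Any AE, placebo | Any AE, empagliflozin | Difference shown, no true difference | Difference shown, true excess of 5 points (65% v 60%) |
|---|---|---|---|---|
| 5% v 2% | 62.0% | 60.8% | −1.2 | +3.7 |
| 10% v 2% | 64.0% | 60.8% | −3.2 | +1.7 |
| 15% v 3% | 66.0% | 61.2% | −4.8 | +0.05 |
| 20% v 5% | 68.0% | 62.0% | −6.0 | −1.25 |

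The any-AE columns are for p = 60% in both arms. For the last column, empagliflozin is 1 − 0.35 × (1 − h); for example 1 − 0.35 × 0.98 = 65.7%, against 64.0% on placebo.

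**A larger true excess.** With other AEs in 70% on empagliflozin and 60% on placebo (+10 points), the row shows +8.6 at 5% v 2%, +6.6 at 10% v 2% and +2.9 at 20% v 3%. With 2% on empagliflozin, full cancellation needs 1 − (0.30 × 0.98) / 0.40 = 26.5% on placebo. Complete masking of a 10-point excess is therefore unlikely; dilution is the realistic effect.

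**Dependence.** If every patient with a glycaemic AE also had another AE, the shift would be zero. Clustering therefore makes the figures above too large.

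**Discontinuation.** If 3% or 5% of placebo patients stopped for hyperglycaemia and were also counted as AE discontinuations, that is 0.03 × 64 = 1.9 or 0.05 × 64 = 3.2 patients. Nothing in the documents says they would be counted, and nothing says they would not.

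**Precision.** For proportions near 60% with 64 per arm, the 95% half-width of a difference is 1.96 × √(2 × 0.6 × 0.4 / 64) = 17.0 points.

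**The case against.** The case against is substantial, and most of it narrows the point.

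- **A reader might infer that every AE summary is contaminated, or that a specific harm is hidden.** The SAP does not support that. Glycaemic terms have their own rows in the SOC/PT table. The hypoglycaemia tables (7.8.1.3) and the AESI, renal and hepatic SMQ, DKA, amputation and muscle-weakness tables (7.8.1.4) are defined without hyperglycaemia terms. An excess of a particular event stays visible. This stands.
- **The recording rule is not an error.** It follows from the protocol's broad AE definition, and nothing here asks for a change to it. This stands.
- **Glycaemic AEs may be uncommon.** Protocol 3.2 considers the risk of significant hyperglycaemia low because background treatment continues, and glucose findings need the investigator's judgement of relevance to become AEs. Hence the 5% v 2% case belongs in the range. For the same reason it is too strong to say that the primary endpoint is counted again: a small HbA1c rise is not automatically an AE.
- **A reader might infer that failed-rescue stops are counted twice.** Protocol 3.3.4.1 assigns them to lack of efficacy. The SAP does not say whether an accompanying hyperglycaemia AE also enters the discontinuation table, and the sponsor guideline it cites for AE presentation is not available. Double counting is open, not shown.
- **The drug-related table.** The documents give no reason why blinded investigators would attribute worsening diabetes to study drug, so that table is left out of the point.
- **Noise.** Safety is descriptive with no hypothesis tests (protocol 7.2.5), and the half-width of about 17 points exceeds the shift in every row of the table. True, but the half-width describes random error. The shift is systematic, and descriptive tables are read from their point estimates.

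**Conclusion.** The point holds for the pooled patient-level totals: any AE, AEs by intensity and, unless the SAP clarifies it, AEs leading to discontinuation. These include efficacy failures expected mainly on placebo and can dilute an overall AE excess on empagliflozin. The plan offers no total from which a reader could remove the effect.

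The size rests on assumed rates, independence and 60% other AEs per arm: about 1 point at 5% v 2%, and 3.2 to 6.0 points from 10% v 2% to 20% v 5%. It is less if glycaemic and other AEs occur in the same patients. Specific safety signals are not concealed, and no test or sample-size figure is affected. The severity is minor.

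**What to change.** In SAP 7.8.1.2:

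1. Before treatment information is released (SAP 8), fix a list of glycaemic-worsening preferred terms, for example hyperglycaemia, blood glucose increased, glycosylated haemoglobin increased and diabetes mellitus inadequate control. Leave DKA out of the list so that it is still counted. A list chosen after unblinding would be open to selection.
2. Add a supplementary version, without those terms, of the overall AE summary, the intensity table and the table of AEs leading to discontinuation.
3. Exclude by preferred term, not by the lack-of-efficacy reason code. Removing stops by reason code could drop a patient whose concurrent non-glycaemic AE also led to the stop.
4. State whether a hyperglycaemia AE that accompanies a stop classified as lack of efficacy enters the main AE-discontinuation table.

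AE collection and the main tables stay as planned. The SAP already uses both tools: a fixed PT list for muscle weakness (7.8.1.4) and analyses repeated under a second definition for SARS-CoV-2 infection (7.8.1.8). The cost is one SAP paragraph and three extra tables, with a slightly longer safety output.

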5.2.6.1.2 Serious adverse event

A serious adverse event (SAE) is defined as any AE, which fulfils at least one of the following criteria:

- results in death,

Proprietary confidential information © 2020 Boehringer Ingelheim International GmbH or one or more of its affiliated companies

- is life-threatening, which refers to an event in which the patient was at risk of death at the time of the event; it does not refer to an event that hypothetically might have caused death if more severe,
- requires inpatient hospitalisation or prolongation of existing hospitalisation
- results in persistent or significant disability or incapacity,
- is a congenital anomaly / birth defect,
- is deemed serious for any other reason if it is an important medical event when based on appropriate medical judgement which may jeopardise the patient and may require medical or surgical intervention to prevent one of the other outcomes listed in the above definitions. Examples of such events are intensive treatment in an emergency room or at home for allergic bronchospasm, blood dyscrasias or convulsions that do not result in hospitalisation or development of dependency or abuse.

AEs which possibly lead to disability will be reported as SAEs as “deemed serious for any other reason”.

5.2.6.1.3 AEs considered “Always Serious”

In accordance with the European Medicines Agency initiative on Important Medical Events, Boehringer Ingelheim has set up a list of AEs, which by their nature, can always be considered to be “serious” even though they may not have met the criteria of an SAE as defined above.

The latest list of “Always Serious AEs” can be found in the electronic data capture system. A copy of the latest list of “Always Serious AEs” will be provided upon request. These events should always be reported as SAEs as described in Section [5.2.6.2](#).

Cancers of new histology and exacerbations of existing cancer must be classified as a serious event regardless of the time since discontinuation of the drug and must be reported as described in Section 5.2.6.2, subsections “AE Collection” and “**AE reporting to sponsor and timelines**”.

5.2.6.1.4 Adverse events of special interest

The term AESI relates to any specific AE that has been identified at the project level as being of particular concern for prospective safety monitoring and safety assessment within this trial, e.g., the potential for AEs based on knowledge from other compounds in the same class. AESIs need to be reported to the sponsor’s PV Department within the same timeframe that applies to SAEs, please see Section [5.2.6.2.2](#).

The following are considered as AESIs:

Hepatic injury

A hepatic injury is defined by the following alterations of hepatic laboratory parameters:

Proprietary confidential information © 2020 Boehringer Ingelheim International GmbH or one or more of its affiliated companies

- an elevation of AST (Aspartate Aminotransferase) and/or ALT (Alanine Aminotransferase) ≥ 3 fold ULN combined with an elevation of total bilirubin ≥ 2 fold ULN measured in the same blood draw sample, or
- aminotransferase (ALT, and/or AST) elevations ≥ 5 fold ULN.

These lab findings constitute a hepatic injury alert and the patients showing these lab abnormalities need to be followed up according to the “DILI checklist” provided in the ISF.

In case of clinical symptoms of hepatic injury (icterus, unexplained encephalopathy, unexplained coagulopathy, right upper quadrant abdominal pain, etc.) without lab results (ALT, AST, total bilirubin) available, the investigator should make sure these parameters are analysed, if necessary in an unscheduled blood test. Should the results meet the criteria of hepatic injury alert, the procedures described in the DILI checklist should be followed.

Diabetic ketoacidosis (DKA)

The risk of DKA must be considered in the event of non-specific symptoms such as nausea, vomiting, anorexia, abdominal pain, excessive thirst, difficulty in breathing, confusion, and unusual fatigue or sleepiness.

In case of a suspected DKA, the investigator should ensure that appropriate tests are performed at the earliest opportunity according to Treatment Guide for Diabetes [[R17-1515](#)], such as blood tests (glucose, blood urea nitrogen/creatinine, and ketone) and blood gas test (pH, bicarbonate, anion gap). The results will be collected on the relevant page of the eCRF.

Investigators should also differentiate deteriorating ketosis/DKA from any mild to moderate increase of ketones which may be seen due to the mechanism of action of empagliflozin, especially in the fasted state (e.g., in the morning).

Due to its mechanism of action, empagliflozin may potentially modify the clinical presentation of DKA which may occur at lower plasma glucose levels in patients with DM. The diagnosis of DKA in these patients can be based on arterial pH ≤ 7.30 , serum bicarbonate levels < 15 and measurement of serum betahydroxybutrate levels. Other diagnostic criteria which can support the diagnosis of DKA are urine ketones and anion gap > 10 .

Investigators should note that not all criteria mentioned above need to apply for the diagnosis of DKA, and clinical judgment should also be taken into consideration.

Decreased renal function

Decreased renal function is defined by a creatinine value showing a ≥ 2 fold increase from baseline and is above the ULN.

For the AESI “decreased renal function” the patient needs to be followed-up appropriately based on local clinical guidance.

Events leading to lower limb amputation

Any event leading to a lower limb procedure of amputation, auto-amputation or disarticulation as defined below is considered as an AESI.

Amputation is a resection of a limb through a bone. Disarticulation is a resection of a limb through a joint. Auto-amputation is a spontaneous separation of non-viable portion of the lower limb.

Not included in this definition are debridement (removal of callus or dead tissue), procedures on a stump (like stump revision, drainage of an abscess, wound revision etc.) and other procedures (e.g., nail resection or removal) without a concomitant resection of a limb (amputation or disarticulation). (International Working Group of Diabetic Foot, 2015).

Each lower limb amputation, disarticulation, or auto-amputation should be reported separately. The SAE report should include the date of the procedure, the level of amputation or disarticulation, the medical condition(s) leading to the procedure and if the patient had some of the known risk factor(s) for lower limb amputation.

5.2.6.1.5 Intensity (severity) of AEs

The intensity (severity) of the AE should be judged based on the following:

Mild: Awareness of sign(s) or symptom(s) that is/are easily tolerated.
Moderate: Sufficient discomfort to cause interference with usual activity.
Severe: Incapacitating or causing inability to work or to perform usual activities.

5.2.6.1.6 Causal relationship of AEs

Medical judgement should be used to determine whether there is a reasonable possibility of a causal relationship between the adverse event and the given study treatment, considering all relevant factors, including pattern of reaction, temporal relationship, de-challenge or re-challenge, confounding factors such as concomitant medication, concomitant diseases and relevant history.

Arguments that may suggest that there is a reasonable possibility of a causal relationship could be:

- The event is consistent with the known pharmacology of the drug.
- The event is known to be caused by or attributed to the drug class.
- A plausible time to onset of the event relative to the time of drug exposure.
- Evidence that the event is reproducible when the drug is re-introduced.
- No medically sound alternative aetiologies that could explain the event (e.g., pre-existing or concomitant diseases, or co-medications).
- The event is typically drug-related and infrequent in the general population not exposed to drugs (e.g., Stevens-Johnson syndrome).
- An indication of dose-response (i.e., greater effect size if the dose is increased, smaller effect size if dose is reduced).

Arguments that may suggest that there is no reasonable possibility of a causal relationship could be:

- No plausible time to onset of the event relative to the time of drug exposure is evident (e.g., pre-treatment cases, diagnosis of cancer or chronic disease within days/weeks of drug administration; an allergic reaction weeks after discontinuation of the drug concerned).
- Continuation of the event despite the withdrawal of the medication, taking into account the pharmacological properties of the compound (e.g., after 5 half-lives). Of note, this criterion may not be applicable to events whose time course is prolonged despite removing the original trigger.
- Additional arguments amongst those stated before, like alternative explanation (e.g., situations where other drugs or underlying diseases appear to provide a more likely explanation for the observed event than the drug concerned).
- Disappearance of the event even though the trial drug treatment continues or remains unchanged.

